#### 8.4 Assessments for safety

The timing of the assessments and procedures are specified in the flow chart Section  $\underline{2}$ .

#### 8.4.1 Adverse events

AEs must be recorded at each visit in accordance with the procedures outlined in Section 12.2 and 12.3.

#### 8.4.2 Adverse Events requiring special forms in the eCRF

For some AEs the investigator must fill in special forms in the eCRF. The AEs that require special forms in the eCRF are

• Pancreatitis

Protocol	
Trial ID: NN9828-4150	
UTN: U1111-1154-7172	
EudraCT no.: 2014-001215-39	

- Thyroid disease
- Neoplasm
- Hypersensitivity reactions
- Injection/Infusion site reactions

If the subject experiences a hyperglycaemic or hypoglycaemic episode the subject should report this in the e-diary.

Hyperglycaemia and hypoglycaemia will only be reported on an AE form if they fulfil the criteria of a SAE.

In case any of these events fulfil the criteria for a SAE, please report accordingly (see Section 12.1)

Some events may require additional assessments as described in the following section.

# 8.4.2.1 Pancreatitis

If an event of pancreatitis (or clinical suspicion of pancreatitis) is observed during the trial, this must be recorded as an AE and on a specific Pancreatitis event form in the eCRF. The following information must be reported if available:

- Signs and symptoms of pancreatitis
- Specific laboratory test supporting a diagnosis of pancreatitis:
  - Amylase
  - Lipase
  - ALAT and ASAT
  - Bilirubin
  - Alkaline Phosphatase
- Imaging performed and consistency with pancreatic disease
- Complications to the event
- Relevant risk factors for pancreatic disease including
  - History of gall-stones
  - History of pancreatitis
  - Family history of pancreatitis
  - Trauma

# 8.4.2.2 Thyroid disease

If an event of thyroid disease, including any thyroid neoplasms is observed during the trial, this must be recorded as an AE and on a specific thyroid disease event form in the eCRF. The following information must be reported if available:

Protocol		Date:	07 May 2015	Novo Nordisk
Trial ID: NN9828-4150	CONFIDENTIAL	Version:	2.0	
UTN: U1111-1154-7172	CONFIDENTIAL	Status:	Final	
EudraCT no.: 2014-001215-39		Page:	59 of 141	

- History of thyroid disease
- Signs and symptoms leading to investigations of thyroid disease
- Specific laboratory tests describing Thyroid function including :
  - Thyroid-stimulating hormone (TSH)
  - Total and free T3 and T4 and Free Thyroid Index
  - Calcitonin
  - Thyroid Peroxiodase antibodies
  - Thyroglobulin and Thyroglobulin antibody
  - Thyroid Stimulating Hormone receptor antibody
- Diagnostic imaging performed and any prior imaging supporting the disease history
- Pathologic examinations
- Treatment given for the condition
- Risk factors identified
- Family history of thyroid disease

#### Thyroidectomy and genetic testing

For Israel: the following is not applicable.

In case a subject is to undergo a thyroidectomy (partial or total) for any reason during the trial, the subject will be asked to inform the investigator prior to the operation. Prior to the thyroidectomy, the subject will be asked to consent to the following:

If assessment of the thyroid gland confirms C-cell pathology (i.e., hyperplastic or neoplastic thyroid C-cells) a blood sample is collected and analysed to identify germline *RET* gene mutations associated with MEN2 syndrome if allowed by local law. The blood sample should be collected at the first visit to the clinic after the confirmation of C-cell pathology. The identification of the gene mutations will be performed by the central laboratory (for details please see Attachment I). The blood sample will be destroyed after analysis.

#### 8.4.2.3 Neoplasm

All events of neoplasm (excluding thyroid neoplasm which should be recorded according to Section 8.4.2.2) must be reported including malignant neoplasm, in situ neoplasm and benign neoplasm observed during the trial. This must be recorded as an AE and on a specific neoplasm event form in the eCRF. The following information must be reported if available:

**CONFIDENTIAL** 

Date: Version: Status: Page: 07 May 2015 2.0 Final 60 of 141

- Type of neoplasm
- Symptoms leading to identification of event
- Diagnostic imaging
- Pathological examination results
- Treatment for the event
- Participation in screening programs
- Risk factors associated to the event

#### 8.4.2.4 Hypersensitivity reactions

If suspicion of a hypersensitivity reaction occurs the subjects should be instructed to contact the site staff as soon as possible for further guidance.

All events of hypersensitivity reactions must be reported as an AE and on a specific hypersensitivity reaction event form in the eCRF. The following information must be obtained:

- Signs and symptoms associated to the event
- Time of appearance after administration of trial drug
- If any relevant immunological tests has been performed and type and result of test
- If any treatment was given for the reaction
- Any previous history of similar reactions
- Any relevant risk or confounding factors identified

Treatment should be according to local practice.

In the event of a severe immediate hypersensitivity reaction to trial product, blood sampling for special laboratory assessment of anti-NNC0114-0006 and anti-liraglutide IgE antibodies and anti-NNC0114-0006 and anti-liraglutide binding antibodies should be conducted at 2 weeks and between 3 and 6 month after the event.

In the event of an immediate systemic hypersensitivity reaction to trial product it is recommended locally to test for tryptase (total and/or mature tryptase) within 3 hours of the reaction. Moreover, a baseline tryptase measurement is necessary  $\sim$ 1 week after the immediate severe hypersensitivity reaction due to individual to individual variation in tryptase baseline concentration.

Tryptase concentrations (if measured) as well as anti-NNC0114-0006 and anti-liraglutide IgE antibodies will not be reported to the trial database but be reported to Novo Nordisk Safety Operations for inclusion in the ARGUS Safety database. Results will be included in the narratives.

# 8.4.2.5 Injection/Infusion site reactions

Protocol		Date:	07 May 2015	Novo Nordisk
Trial ID: NN9828-4150	CONFIDENTIAL	Version:	2.0	
UTN: U1111-1154-7172	CONFIDENTIAL	Status:	Final	
EudraCT no.: 2014-001215-39		Page:	61 of 141	

All events of injection site/Infusion site reactions caused by NNC0114-0006 and liraglutide must be reported as an AE and on a specific injection site reaction event form in the eCRF. The following information must be obtained:

- Type of reaction local or generalised
- Symptoms associated to the event
- Treatment for the event
- Association with the trial product(s)
- Risk factors associated to the event

Treatment should be according to local practice.

#### 8.4.2.6 Hyperglycaemic episodes

A hyperglycaemic episode is defined as, and confirmed by PG values >16.7 mmol/l (300 mg/dl).

PG should always be measured when there is a suspicion of a hyperglycaemic episode. Multiple (>1) hyperglycaemic values of SMPG >16.7 mmol/l (300 mg/dl) are considered as one hyperglycaemic episode until the SMPG is <16.7 mmol/L (300 mg/dl). One episode is set to a maximum of 24 h for the first SMPG >16.7 mmol/l (300 mg/dl).

All PG values >16.7 mmol/l (300 mg/dl) should be recorded by the subject in the e-diary from visit 2 to visit 89.

The recording should include the following information (layman-language will be used in the ediary to phrase the respective questions ensuring that subjects understand the questions):

- Date and time of hyperglycaemic episode
- The PG level before treating the episode
- Blood ketone value before treating the episode
- Date, time and dose of last liraglutide/placebo administration prior to the episode
- Date, time and dose of last basal insulin administration prior to the episode
- Date, time and dose of last bolus insulin administration prior to the episode
- Whether the episode was symptomatic
- Where there any factors contributing to the hyperglycaemic episode?
  - Recent changes in diet
  - Concomitant infection
  - Recently missed or reduced dose of insulin
  - Other
  - Unknown

Protocol Trial ID: NN9828-4150	CONFIDENTIAL	Date: Version:	07 May 2015 2.0	Novo Nordisk
UTN: U1111-1154-7172 EudraCT no.: 2014-001215-39		Status: Page:	Final 62 of 141	

The subject should measure his/her plasma ketones when plasma glucose values >16.7 mmol/l (300 mg/dl). Subjects will be instructed in how to record the results of the ketone values in the provided e-diaries and should only record the ketone values based on the glucometer measurements.

If the hyperglycaemic episode fulfils the criteria for an SAE then an AE form and a SIF must also be completed in the eCRF.

# Assessments in case of suspicion of treatment emergent hyperglycaemia and diabetic ketoacidosis

Inadequate dosing or discontinuation of insulin treatment may lead to hyperglycaemia and DKA. Usually the first symptoms of hyperglycaemia develop gradually over a period of hours or days. Symptoms may include: increased thirst, dry mouth, increased frequency of urination, headache, fatigue, blurred vision, or even nausea, vomiting, abdominal pain, drowsiness, flushed dry skin, loss of appetite, flushing, confusion, difficulty breathing as well as acetone odour of breath. Untreated hyperglycaemia eventually lead to DKA, which is potentially lethal. Illness, such as infections and fever may lead to increased insulin requirement.

If a subject suspects hyperglycaemia, the subject must perform plasma glucose measurement immediately. If SMPG > 16.7 mmol/l (300 mg/dl), plasma ketones should be measured.

Normally, ketone levels are expected to be less than 0.6 mmol/l. Ketone levels may increase if a person fasts, exercises vigorously or has diabetes and becomes ill. If plasma ketone levels are higher than 1.5 mmol/l, subjects will be instructed to contact the site staff immediately for advice and assistance.

If the investigator suspects DKA, confirmatory tests and appropriate treatment should be initiated. A DKA is confirmed if at a minimum three of the following 5 diagnostic criteria are present  $\frac{32}{2}$ :

1. PG > 13.9 mmol/l (250 mg/dl)

2. Arterial pH < 7.30

3. Serum Bicarbonate < 18 mEq/l

4. Serum Ketones: Positive. If available, measurement of plasma hydroxybutyrate may be useful for diagnosis 3-hydroxybutyrate > 1.5 mmol/l

5. Urine Ketones: Positive

Confirmed cases of DKA must be reported as SAEs by completion of an AE and SIF in the eCRF and should be followed-up with investigations of potential precipitating causes of DKA (i.e. infection/stroke/acute myocardial infarction/pancreatitis).

Protocol
Trial ID: NN9828-4150
UTN: U1111-1154-7172
EudraCT no.: 2014-001215-39

CONFIDENTIAL

Date: Version: Status: Page:

# 8.4.2.7 Hypoglycaemic episodes

Blood glucose should always be measured and recorded when a hypoglycaemic episode is suspected.

All plasma glucose values:

- $\leq 3.9 \text{ mmol/l} (70 \text{ mg/dl}) \text{ or}$
- > 3.9 mmol /l (70 mg/dl) occurring in conjunction with hypoglycaemic symptoms

should be reported according to the instructions below throughout the trial from visit 2 to visit 89. Upon onset of a hypoglycaemic episode the subject is recommended to measure blood glucose every 15 minutes in accordance to current guidelines  $\frac{33}{2}$ .

A SMPG  $\leq$ 3.9 mmol/l (70 mg/dl) or hypoglycaemic symptoms must trigger a hypoglycaemic episode form to be completed by the subject. Repeated SMPG measurements and/or symptoms will per default be considered as one hypoglycaemic episode until a succeeding measurement is >3.9 mmol/l (70 mg/dl) or symptoms have been resolved. One hypoglycaemic episode form is to cover these measurements and/or symptoms. However, each hypoglycaemic episode form will cover a period of maximum 60 minutes after onset of a hypoglycaemic episode.

In case of several low SMPG values within the 60 minute interval, the lowest value is the one that will be reported as the SMPG value for the hypoglycaemic episode but the start time of the episode will remain as the time for the first SMPG value and/or symptom.

If a new low SMPG value is measured or the subject still has symptoms more than 60 minutes after the first reported low SMPG value it is considered as a new episode and a new hypoglycaemic episode form is to be filled in.

The record should include the following information (layman-language will be used in the e-diary to phrase the respective questions ensuring that subjects understand the questions):

- Date and time of hypoglycaemic episode
- The plasma glucose level before treating the episode (if available) and any follow up measurements. (The lowest value measured during the hypoglycaemic episode will be reported as the SMPG value for the episode, the remaining values will be kept as source data).
- Whether the episode was symptomatic (Yes/No). (A hypoglycaemic episode starting as non-symptomatic should be updated to symptomatic if the subject experiences symptoms later during the episode. The subjects are therefore to be prompted whether there are changes to symptoms for each low SMPG value within the 60 minutes period).

Protocol		Date:	07 May 2015	Novo Nordisk
Trial ID: NN9828-4150	CONFIDENTIAL	Version:	2.0	
UTN: U1111-1154-7172	CONFIDENTIAL	Status:	Final	
EudraCT no.: 2014-001215-39		Page:	64 of 141	

- Whether the subject was able to treat him/herself (If the severity of a hypoglycaemic episode aggravates, only one hypoglycaemic episode should be reported reflecting the most severe condition. The subjects are therefore to be prompted whether they are able to self-treat (Yes or No) for each low SMPG value within the 60 minutes period).
- Date, time and dose of last liraglutide/placebo administration prior to the episode
- Date, time and dose of last basal insulin administration prior to the episode
- Date, time and dose of last bolus insulin administration prior to the episode
- Date and time of last main meal prior to episode
- Whether the episode occurred in relation to physical activity
- Any sign of fever or other disease
- Whether the subject was asleep when the episode occurred If yes, whether the symptoms of the episode woke up the subject

The answer to the question: "Was subject able to treat him/herself?" must be answered "No" for an episode requiring assistance of another person to actively administer carbohydrate, glucagon, or take other corrective actions. Plasma glucose concentrations may not be available during an event, but neurological recovery following the return of plasma glucose to normal is considered sufficient evidence that the event was induced by a low plasma glucose concentration  $\frac{33}{2}$ .

Oral carbohydrates should not be given if the subject is unconscious.

If the question "Was the subject able to treat him/herself?" is answered "No", the following information should be recorded:

- Who helped manage the episode (medical person or non-medical person)
- Where the treatment was administered (in clinic/ emergency room/ hospital or other. If the subject was treated in clinic/ emergency room/ hospital whether they were transported in an ambulance or not)
- Type of treatment provided by other person (i.e. oral carbohydrates, glucagon, IV glucose or other)
- Were symptoms alleviated after administration of treatment?
- Factors contributing to the episode (i.e. physical activity, missed meal, diet changed, medication error (i.e. overdose, mix-up between products), miscalculation of insulin dose, other or unknown)
- Did the subject experience seizure?
- Was the subject unconscious/comatose?
- Did the subject experience any of the following symptoms 34:
  - Autonomic: sweating, trembling, hunger or palpitations
  - Neuroglycopenic: confusion, drowsiness, speech difficulty, visual disturbances, odd behaviour, impaired balance or incoordination

CONFIDENTIAL

Date: Version: Status: Page:

- General malaise: headache or malaise
- Did the subject experience other symptoms?

The Investigator must review the e-diary data for correct reporting of SMPGs and hypoglycaemic episodes at each contact. If the investigator experiences missing data in the diary, the subject must be questioned whether there have been any severe hypoglycaemic episodes since the last visit i.e. any hypoglycaemic episodes where the subject was not able to self-treat. Any severe hypoglycaemic episodes must be reported on a hypoglycaemic episode form.

Non-severe hypoglycaemic episodes not having a hypoglycaemic episode form completed within 7 days since the SMPG measurement will not be reported retrospectively and missing data points for non-severe hypoglycaemic episodes will generally not be questioned by the investigator or queried by Novo Nordisk due to subject's short recall of non-severe hypoglycaemic episodes  $\frac{35,36}{2}$ .

The subject must be re-trained in how to report hypoglycaemic episodes if the investigator identifies unreported hypoglycaemic episodes.

If the hypoglycaemic episode fulfils the criteria for an SAE and/or a medical event of special interest (MESI) then an AE form and a safety information form must also be filled in, see section 12.1.

# 8.4.3 Technical complaints

Technical complaints must be recorded in accordance with the procedures outlined in Section 12.4. The following information has to be recorded:

- Product
- Code no
- DUN
- Onset date of technical complaint
- Description of the technical complaint

#### 8.4.4 Body measurements

#### 8.4.4.1 Height

Height without shoes should be measured in meters (m) or inches (in) and recorded with two decimals at screening (V1).

#### 8.4.4.2 Body weight

Body weight should be measured and recorded according to Section  $\underline{2}$ .

Protocol		Date:	07 May 2015	Novo Nordisk
Trial ID: NN9828-4150	CONFIDENTIAL	Version:	2.0	
UTN: U1111-1154-7172		Status:	Final	
EudraCT no.: 2014-001215-39		Page:	66 of 141	

Body weight should be measured in kilograms (kg) or pounds (lb) and should be recorded with one decimal in the eCRF. The body weight should be measured with an empty bladder, without shoes and only wearing light clothes.

Body weight should be measured using a calibrated scale. The same scale should preferably be used throughout the trial.

# 8.4.4.3 BMI

BMI will be calculated at the first visit by the eCRF using the equation:

BMI kg/m^2 = Body weight (kg)/ (Height (m) x Height (m)) or  $(kg/m^2 = (lb/in^2 x 703))$ 

# 8.4.5 Electrocardiogram

A 12-lead ECG must be performed locally by the investigator or delegated staff at the time points specified in Section 2. The ECG print out must be interpreted, signed and dated by the investigator.

The evaluation must follow the categories:

- Normal
- Abnormal
  - Was the result clinically significant? (Yes/No)

A baseline ECG performed for any reason unrelated to the trial within 30 days prior to Visit 1 is acceptable provided no clinical symptoms suggestive of cardiac disease have occurred in the meantime. If the ECG is performed before the subject has signed the informed consent form, it must be documented in the medical records that the reason for performing the procedure was not related to this trial.

Any abnormal, clinical significant findings at screening visit (Visit 1) must be recorded as concomitant illness.

Any clinical significant worsening from Visit 1 must be recorded as an AE (see Section 12.1)

In the treatment period of the trial the following information has to be recorded:

- Overall interpretation
- Heart rate
- PR interval
- QRS duration
- QTc interval
- RR interval

In the observation period of the trial the following information has to be recorded:

Protocol Trial ID: NN9828-4150 UTN: U1111-1154-7172 EudraCT no : 2014-001215-39	CONFIDENTIAL	Date: Version: Status: Page:	07 May 2015 2.0 Final 67 of 141	Novo Nordisk
EudraCT no.: 2014-001215-39		Page:	67 of 141	

• Overall interpretation

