#### 8.1.5 Investigator's assessment

It is the responsibility of the investigator or delegated staff to review the e-diaries, PROs, ECGs, eye examinations (fundoscopy/ fundus photography), laboratory reports etc. This must be documented with the investigator or delegated staff's dated signature either on the front page of the documents and/or in the subject's medical records. The signed documents must be retained at the investigator site as source documentation.

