## 24 Retention of clinical trial documentation and human biospecimens

## 24.1 Retention of clinical trial documentation

Subject's medical records must be kept for the maximum period permitted by the hospital, institution or private practice.

The investigator must agree to archive the documentation (this includes both electronic and paperbased records) pertaining to the trial in an archive after completion or discontinuation of the trial if not otherwise notified. The investigator should not destroy any documents without prior permission from Novo Nordisk. If the investigator cannot archive the documents at the trial site, Novo Nordisk can refer the investigator to an independent archive provider that has a system in place to allow only the investigator to access the files.

The investigator must be able to access his/her trial documents without involving Novo Nordisk in any way. Site-specific CRFs and other subject data (in an electronic readable format or as paper copies or prints) will be provided to the investigator before access is revoked to the systems and/or electronic devices supplied by Novo Nordisk. These data must be retained by the trial site. If the provided data (e.g. the CD-ROM) is not readable during the entire storage period, the investigator can request a new copy. A copy of all data will be stored by Novo Nordisk.

Novo Nordisk will maintain Novo Nordisk documentation pertaining to the trial for as long as the product is on the market plus 20 years.

The files from the trial site/institution must be retained for 15 years after the completion of the trial, or longer if required by local regulations or Novo Nordisk. In any case trial files cannot be destroyed until the trial site/institution is notified by Novo Nordisk. The deletion process must ensure confidentiality of data and must be done in accordance with local regulatory requirements.

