### **Supportive secondary safety endpoints**

- Number of treatment emergent adverse events reported
  - from first dose of trial product to week 54
  - from week 54 to week 80
- Number of treatment emergent hyperglycaemic episodes
  - from first dose of trial product to week 54
  - from week 54 to week 80
- Number of treatment emergent episodes of diabetic ketoacidosis (DKA)
  - from first dose of trial product to week 54\*
  - from week 54 to week 80
- Number of subjects experiencing treatment emergent injection/infusion site reactions from first dose of trial product and during treatment period (54 weeks) caused by:
  - NNC0114-0006/liraglutide/placebo injection/infusion
- Number of treatment emergent hypoglycaemic episodes according to the American Diabetes Association (ADA) and Novo Nordisk definitions
  - from first dose of trial product to week 54\*
  - from week 54 to week 80
- Change in body weight from baseline to week 54 and week 80
- Diabetes complications (retinopathy and estimated glomeruli filtration rate) from baseline to week 54 and week 80
- Change in laboratory safety variables (haematology, biochemistry, coagulation, lipids, IgE, urine dipsticks, cytokine panel, and hormones), vital signs, electrocardiograms (ECGs), eye-examination and outcome of physical examination from baseline to week 54 and week 80
- Change in anti-NNC0114-0006 antibodies from baseline to week 54 and week 80
- Change in anti-liraglutide antibodies from baseline to week 54 and week 80

\* Key supportive secondary endpoint prospectively selected for disclosure (e.g. clinicaltrials.gov and EudraCT)

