## Vital signs and ECG

The systolic blood pressure, diastolic blood pressure and pulse endpoints will be analysed using a similar model as described for the primary endpoint except that the corresponding value at baseline will be included as a covariate and the analysis will be made on the original scale. Consequently, treatment means (LSMeans) and treatment differences will be presented with 95% CIs.

All endpoints will be summarised. The numerical endpoints will be presented graphically.

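### The ECG record keeps a local QTc but neither uncorrected QT nor the correction formula, so QTc summaries by arm can carry a heart-rate artefact

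*Protocol*

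**What the plan says.** Protocol Section 8.4.5 places the test at the sites: "A 12-lead ECG must be performed locally by the investigator or delegated staff at the time points specified". Of the output it says "The ECG print out must be interpreted, signed and dated by the investigator". No central reader and no device standard is mentioned, and Section 5.1 describes a multi-centre, multinational trial.

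The same section continues "In the treatment period of the trial the following information has to be recorded" and lists an overall reading, heart rate, and the PR, QRS, QTc and RR measurements. For the observation period it lists the overall reading alone. Uncorrected QT appears in neither list, and no QT correction formula is given in either document.

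ECG change is a supportive secondary safety endpoint in Protocol Section 4.2.2.2 and SAP Section 1.1.2.2, which cover "vital signs, electrocardiograms (ECGs), eye-examination and outcome of physical examination from baseline to week 54 and week 80". SAP Section 2.4.1.2, under Vital signs and ECG, models blood pressure and pulse by arm. For everything else there it says "All endpoints will be summarised. The numerical endpoints will be presented graphically".

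Two retention rules matter here. Section 8.1.5 names ECGs among the documents that the investigator reviews and adds "The signed documents must be retained at the investigator site as source documentation". Section 24.1 adds "The files from the trial site/institution must be retained for 15 years after the completion of the trial".

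**The concern.** QTc is a derived quantity, and its value depends on the formula as well as on the heart. Elsewhere the protocol fixes such rules: Section 8.4.4.3 gives the BMI equation, and Section 8.5.2.4 assigns eGFR to the central laboratory with a named equation. For QTc the rule is left to whatever each site's machine prints.

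Some correction formulas leave a residual dependence on heart rate. Where one of these is in use, a treatment that changes rate will also change QTc, even with unaltered repolarisation. Randomisation does not remove this, because the rate change would itself follow the treatment. Taking change from baseline cancels a constant formula, but not its rate-dependent part. Nothing in Section 8.4.5 asks for the same machine at each visit either.

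At stake is a display of QTc change by arm that suggests a lengthening that is not there, or hides one that is. An analyst holding only the database could not put all values on one footing, because the formula is not a recorded item.

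**Working it through.** The documents give no QT or QTc figure and no heart-rate effect of either drug, so there is nothing of the plan's own to reproduce. The numbers below are an illustration.

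**From the documents:** RR, heart rate and QTc are stored together for treatment-period ECGs; QT and the formula are not.

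**Assumed:** no true repolarisation effect; QT follows the cube-root relation with cube-root QTc held at 400 ms; resting rate 70 bpm; rate rise of 3, 5 or 8 bpm.

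**Formulas**, with RR = 60/rate in seconds:
- QT = 400 × RR^(1/3)
- square-root QTc = QT / RR^(1/2) = 400 × (rate/60)^(1/6)
- cube-root QTc = QT / RR^(1/3) = 400, constant by construction

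**Step 1: size of the artefact at 70 bpm** (differences taken before rounding)

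| Rate (bpm) | RR (s) | QT (ms) | Square-root QTc (ms) | Change from 70 bpm (ms) |
|---|---|---|---|---|
| 70 | 0.857 | 380.0 | 410.4 | – |
| 73 | 0.822 | 374.7 | 413.3 | +2.9 |
| 75 | 0.800 | 371.3 | 415.2 | +4.7 |
| 78 | 0.769 | 366.5 | 417.9 | +7.5 |

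**Step 2: other starting rates and formulas.** With resting rates from 60 to 80 bpm, a rise of 3, 5 or 10 bpm moves square-root QTc by +2.6 to +3.3, +4.3 to +5.4 or +8.3 to +10.4 ms. Over the same grid:
- the linear RR correction, QT + 154 × (1 − RR), moves by −1.2 to +2.0 ms;
- the linear rate correction, QT + 1.75 × (rate − 60), moves by −2.5 to +3.5 ms;
- the cube-root correction moves by 0.

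The artefact is therefore mainly a feature of square-root correction. If only half the ECGs used it and the rest used cube-root, the average shift at 70 bpm would halve, to about +1.4, +2.4 and +3.7 ms.

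**Step 3: can QT be recovered from what is stored?** Take 80 bpm, RR = 0.75 s and a stored square-root QTc of 419.6 ms.
- Formula known: QT = 419.6 × 0.75^(1/2) = 363.4 ms, and cube-root QTc = 363.4 / 0.75^(1/3) = 400.0 ms. The recovery is exact.
- Formula wrongly taken to be cube-root: the stored 419.6 ms is accepted as it stands, an error of 19.6 ms. At 70 bpm and 90 bpm the same mistake gives 10.4 ms and 28.0 ms.

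Stored RR is thus enough once the formula is documented. A wrong guess at the formula does more harm than the artefact itself.

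**The case against.** The strongest case against is that little is lost. RR and heart rate sit beside every treatment-period QTc, the ECG is signed and kept as source for 15 years, and each tracing is judged for clinical significance, with any significant worsening reported as an adverse event. This is a proof-of-principle trial with a C-peptide primary endpoint, not a dedicated QT study. Different formulas at different sites are not confounding in themselves under blinded, central 1:1:1:1 allocation; they mainly add noise.

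Most of that stands, and it rules out three stronger readings that a reader might infer.

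- *That the gap is beyond repair.* Step 3 and the retention rules show otherwise. What remains true is that repair needs the formula or the print-out, and neither is in the database. The documents also do not say that the print-outs show QT.
- *That QTc by arm is confounded, because modelling pulse by arm shows that a rate effect is anticipated.* Pulse shares a routine sentence with systolic and diastolic pressure, and the SAP applies a similar model to TSH, IgE and the cytokine panel. The documents state no heart-rate effect. An artefact needs both such an effect and a rate-sensitive formula at the sites.
- *That the artefact amounts to 1 to 3 standard errors of a treatment comparison.* That would follow from an assumed SD of change of 15 ms and 60 per arm, since 15 × √(2/60) = 2.74 ms. However, no QTc comparison is planned; QTc is only summarised and plotted.

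One could also adjust QTc for the stored rate, but that conditions on a variable measured after treatment and is a poorer answer than one common correction.

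**Conclusion.** The point holds as a cheap improvement. As written, the plan yields summaries of a named safety endpoint built on unknown and possibly mixed correction formulas, and the database alone cannot put them on a common basis.

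The possible distortion is about +3 to +7.5 ms for a rise of 3 to 8 bpm from 70 bpm where square-root correction is used, smaller where only some sites use it, and nil with cube-root. This rests on an assumed rate change, an assumed resting rate, and QT following the cube-root relation; none of these comes from the documents. The consequence is confined to descriptive safety displays. It does not touch the primary endpoint or any planned test.

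A neighbouring gap is separate: the endpoint runs to week 80, but the observation period records only the overall reading, so interval changes at week 80 are not available under any formula.

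**What to change.** - In Protocol Section 8.4.5, add uncorrected QT to the items recorded in the treatment period.
- In SAP Section 2.4.1.2, state that QTc is derived centrally from recorded QT and RR with one pre-specified formula (cube-root, for example), and that summaries and plots by arm use this value rather than the machine's. Choose the formula before the database lock that follows Visit 63, since the sponsor is unblinded after it.
- For ECGs already recorded, recover QT from the retained print-outs where they show it, or from stored QTc and RR once the formula used at the site is documented. Do not assume a formula.

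The cost is one extra eCRF field, one derivation line in the SAP, and some source queries, with no added procedure for subjects. The flow charts schedule eight ECGs per subject from Visit 3 to Visit 63, so full retrieval from print-outs would cover at most 8 × 304 = 2,432 tracings. Asking each site to document its device formula would be the lighter route.
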